9.2 DETERMINATION OF SAMPLE SIZE

The sample size was chosen to have sufficient power to detect a 30% difference in the vAUC, assuming a drop out of approximately 15-20% from the vaccination group. Since there is 15% over-enrolment during the vaccination phase compared to challenge, it is assumed that in a worse-case scenario a 25% reduction, or that the final numbers to undergo challenge per group could be as low as 72 MVA-NP+M1 and 48 Placebo recipients. The placebo vAUC data were estimated using qPCR data accumulated during two previous challenge studies, where vAUC was calculated using the trapezoidal rule. The allocation ratio is chosen not at 2:1 (which would be 80:40), but rather at 80:54 to ensure sufficient placebo recipients within each challenge period to adequately assess the take rate of the challenge for that given cohort. Sample sizes of 80 and 54 participants in the MVA-NP+M1 and placebo groups, respectively, will yield approximately 90% power to detect at least a 22% difference in vAUC at a two-sided, alpha=0.05 level. If enrolment is lower than anticipated, approximately two-thirds of the planned sample size will still yield at least 80% power to detect a 30% difference in vAUC (two-sided alpha = 0.05).

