The primary endpoint upon which the powering analysis is performed using the vAUC from the qPCR for all collected samples, compared between groups using a Mann-Whitney U Test (Wilcoxon rank sum). The assumptions are based on the Placebo data from two prior challenge studies with this H3N2 virus. The study is powered to detect as low as a 20% efficacy of the vaccine using this endpoint at a power of 80%, and approximately 25% efficacy at a 90% power. This allows for up to 20% drop out without prejudicing the goal of the study.

Secondary endpoints include the rate of virologically confirmed ILI (symptoms of either an upper or lower respiratory illness along with two positive PCR or culture) measured between groups. Another key secondary endpoint of relevance to the biologic effect of this vaccine will be the comparison of the symptom severity as a total Area Under the Curve (AUC). This endpoint takes into account both the severity and the duration of symptoms. Mucosal secretions will be collected, and the weight of the sample tissues compared between groups.

Importantly, with a 83% attack rate and 30% efficacy, approximately 20 of the 80 vaccinated participants will have a zero AUC, and these participants can be compared to those with the highest vAUC in correlate of protection analyses.

Safety will be reported using standard frequency and severity tables.

At the protocol sample size, there is a 93% chance that a Serious Adverse Event (SAE) with a 3% incidence will be observed in at least one participant.

TIME AND EVENTS SCHEDULE

Period 1- Screening and Vaccination Schedule

Period 1	Screening 1	Screening 2	Baseline Vaccination	Out patient Clinic Visit	Phone ⁸	Out patient Clinic Visit	Out patient Clinic Visit	Phone ⁸	Unscheduled visit ⁷	See Challenge Day -2	Phone
	Days -42 to -2	Day -21 to -1	Day 1	Day 2	Day 4	Day 8 ±1 (Week 1 Visit)	Day 28 ±3	Day 56 ±3			Month 6 (180 ±14 days) ⁹
Informed Consent	x ¹	x ¹									
Inclusion/Exclusion	x ²	x ²									
Randomization			x								
Medical History/Demography		x									
Physical Examination		x ^{2a}				x	x		x		
Vital Signs		x				x	x		x		
Supine 12-lead ECG		x									
Haematology		x							x		
Biochemistry ^{2b}		x							x		
Microneutralization (MNT) ¹	x	x ¹									
Urinalysis		x							x		
HIV,, Hep C, HBsAg		x									
Urine Drug Screen		x	x						x		
Alcohol breath test		x	x						x		
Serum/Urine Pregnancy ³		x	x						x		
Blood sample for cellular immunogenicity assays PBMCs ⁴ , and Serum			x ^{4a}			x	x				

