Challenge agent dose levels increased per cohort and dosing started at a titre of approximately 10^5 TCID₅₀ (50% tissue culture infective dose/mL). In vivo toxicity, as determined by the established ferret model for Influenza A pathogenesis, suggested that A/Belgium/4217/2015 (H3N2) could be used at similar dosing titres (starting from 10^5 TCID₅₀/mL to 6.76×10^6 TCID₅₀/mL) as those previously used in human challenge trials. Based on international literature, comparing HI titres to MNT, a provisional cut-off for participant inclusion based on a MNT of ≤ 20 was chosen. Since the influence of low MNT (≥ 10) was unknown, volunteers with low MNT were equally distributed over the cohorts

While the lower bound of the required attack rate (>60%) was reached in all cohorts, none of the participants experienced an SAE or cytokine-related AE during the study even at the highest inoculation dose tested. The observed attack rate in all cohorts was well above the lower bound of the required attack rate. The signs and/or symptoms of Influenza infection similar to community acquired disease. Taken together, the data from the first in human dose escalation study show that A/Belgium/4217/2015 (H3N2) is a truly wild-type Influenza A H3N2 strain which, when used as challenge agent, results high attack rates and significant host changes with relatively low variation in virological, haematological, clinical laboratory and symptom efficacy parameters. The choice of challenge dose is dependent on several factors but an intermediate dose (10^6 TCID₅₀/mL) in volunteers with MNT ≤ 10 is adequate given the relatively low variation of essential efficacy parameters observed. Combining all data from further and ongoing studies, the attack rate for this dose with those participants with MNT ≤ 10 has been approximately 90%. Increasing this cut-off to < 20 should have a minimal effect on the predicted attack rate based on previous evidence.

Non-Clinical Studies

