3.2 DISCUSSION OF STUDY DESIGN

Dose Selection

The dose of MVA-NP+M1 to be used in this study will be 1.5×10^8 pfu (4.3×10^8 TCID₅₀) 0.5 mL administered intramuscularly, based on previous Phase 1 and 2a clinical trials, which have shown the vaccine is safe and immunogenic at this dose (FLU001, FLU002, FLU003, FLU004 and FLU005). Participants received the proposed 1.5×10^8 pfu dose in FLU001 which was less reactogenic and better tolerated than the 2.5×10^8 pfu used in one group. The immune responses were not significantly different between the two doses. The 1.5×10^8 pfu dose was thus chosen to balance reactogenicity and immunogenicity.

Placebo Control

Placebo saline control given as 0.5 mL intramuscularly in the deltoid will be used to establish the frequency and magnitude of solicited and non-solicited adverse events, as well as to control for the laboratory and clinical assessments used as endpoints. All such recordings will be performed in a blinded fashion.

Dose of challenge agent

The choice of challenge dose is dependent on several factors but an intermediate dose (10^6 TCID₅₀/mL) in volunteers with MNT <20 is adequate given the relatively low variation of essential efficacy parameters observed. Combining all data from previous and ongoing studies, the attack rate for this dose with those participants with MNT <20 has been approximately 83%.

Randomization and Blinding

Randomization will be used to avoid bias in the assignment of participants to treatment, to increase the likelihood that known and unknown participant attributes (e.g., demographic and baseline characteristics) are evenly balanced across treatment groups, and to enhance the validity of statistical comparisons across treatment groups. Participants are blinded to study allocation.

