9.1.2.3 EXPLORATORY ENDPOINTS

Time to start, time to peak and time to cessation of total symptoms from virus inoculation and duration of total symptoms will be summarized by the Kaplan-Meier method. Differences between the treatment groups will also be tested using the log-rank test.

Total days of fever for MVA-NP+M1 vs. Placebo will be compared by means of a zero-inflated Poisson model. Fever is defined as >38.0 degrees Celsius.

Total mucus production between Days 1 and 11 post-challenge, as measured by total tissue weight, will be compared between vaccine groups using a t-test or Mann-Whitney U Test.

Immunogenicity data, using interferon gamma/granzyme B ELISpot as the primary outcome measure, will be compared between vaccine groups using a t-test or Mann-Whitney U Test. Descriptive statistics will be calculated including number of observations, mean, median, geometric mean titre (GMT), minimum and maximum with 95% confidence interval (CI).

Transcriptional response to vaccination and viral challenge may be assessed by deep sequencing of RNA using PAXgene® RNA tubes.

Epigenetic responses of T-Cells may be assessed during the study, and the methods will be detailed in the SAP.

Descriptive comparison of the ratios of the GMTs of the MNT and HI results between the two treatment groups will be calculated along with the corresponding 95% CI based on the \log_{10} difference of the two groups.

Importantly, with a 83% attack rate and 30% efficacy, approximately 20 of the 80 vaccination participants will have a zero area under the curve, and these participants can be compared to those with the highest vAUC in correlate of protection analyses. An exploratory correlate of protection analysis will be detailed in the SAP prior to breaking the blind on the immunogenicity data.

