1.3 EXPECTED SAMPLE SIZE

The sample size was chosen to have sufficient power to detect a 30% difference in the vAUC, assuming a drop out of approximately 15-20% from the vaccination group. Since there is 15% over-enrolment during the vaccination phase compared to challenge, it is assumed that in a worst-case scenario a 25% reduction, or that the final numbers to undergo challenge could be as low as 72 MVA-NP+M1 and 48 Placebo recipients. The placebo vAUC data were estimated using qPCR data accumulated during two previous challenge studies, where vAUC was calculated using the trapezoidal rule. The allocation ratio is chosen not at 2:1 (which would be 80:40), but rather at 80:54 to ensure sufficient placebo recipients within each challenge period to adequately assess the take rate of the challenge for that given

	Statistical Analysis Plan	
FLU010	Final analysis	Final 3.0 of 15JUN2020

cohort. Sample sizes of 80 and 54 participants in the MVA-NP+M1 and placebo groups, respectively, will yield approximately 90% power to detect at least a 22% difference in vAUC at a two-sided, alpha=0.05 level. If enrolment is lower than anticipated, approximately two-thirds of the planned sample size will still yield at least 80% power to detect a 30% difference in vAUC (two-sided alpha = 0.05).

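### The protocol's 20 of 80 vaccinees with zero AUC is the number of infections prevented; on its own inputs the zero-AUC count is about 34, and the power figures lack one stated basis at the 83% attack rate

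*Protocol*

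**What the plan says.** **Zero-AUC count.** The synopsis (Statistical Methods) and Section 9.1.2.3 combine an 83% attack rate with 30% efficacy and conclude that "approximately 20 of the 80 vaccination participants will have a zero area under the curve" (Section 9.1.2.3; the synopsis is near-identical). Both propose comparing these participants with those who have the highest vAUC in a correlate-of-protection analysis.

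**Power.** The synopsis bases the sample size on a challenge cohort of 134. It says that the study can detect as little as "a 20% efficacy of the vaccine using this endpoint at a power of 80%, and approximately 25% efficacy at a 90% power", followed by an allowance for up to 20% drop-out. Section 9.2 opens with a 30% difference in vAUC as the design target. For 80 vaccinees against 54 placebo recipients, its claim is that this design "will yield approximately 90% power to detect at least a 22% difference in vAUC at a two-sided, alpha=0.05 level". It adds that two-thirds of the sample still gives at least 80% power for 30%. SAP 1.3 repeats the Section 9.2 figures ("will yield approximately 90% power to detect at least a 22% difference in vAUC").

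**Attack rate.** The version 5.0 entry in the protocol history records a change from 90% to 83%. Among the affected places it lists the synopsis statistics and Section 9.1.2.3, but not Section 9.2. Section 3.2 says that the attack rate at MNT below 20 "has been approximately 83"%. Section 1.1 gives about 90% for MNT of 10 or less and says that raising the cut-off "should have a minimal effect on the predicted attack rate based on previous evidence".

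**The concern.** The zero-AUC sentence appears to multiply attack rate by efficacy and stop there. That counts vaccinees whom the vaccine saved from infection. It leaves out those whom the challenge would not have infected anyway, although they also have zero AUC. Anyone who plans the correlate comparison from this sentence would expect too few zero-AUC vaccinees and would take all of them to be vaccine-protected.

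The power statements give two different effects at 90% power without saying whether they share a sample size. A lower attack rate puts more zeros in both arms, which normally costs power, yet the documents show no power figure tied to 83%. A null primary result would be judged against the stated 90%, so the reader needs to know what that figure assumes.

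**Working it through.** **1. Zero-AUC count.** Inputs from the synopsis and Section 9.1.2.3: 80 vaccinees, attack rate 0.83, efficacy 0.30.

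- Reproducing the plan's figure: 80 × 0.83 × 0.30 = 19.9. This is infections prevented.
- Not infected even without vaccine: 80 × (1 − 0.83) = 13.6.
- Not infected in total: 80 × (1 − 0.83 × 0.70) = 33.5, which is 13.6 + 19.9.
- Share of the zero-AUC group that owes nothing to the vaccine: 13.6 / 33.5, about 40%.
- If the 30% is instead a graded fall in vAUC with no infection prevented, the count is 13.6.

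SAP 5.3.3 sets the log10 viral load to 0 when virus is not detected, so a participant who never has virus detected has vAUC 0. An attack needs at least two positive qPCR swabs, so a participant with a single positive swab is not an attack but has a non-zero vAUC. That would pull 34 down somewhat.

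**2. The two effects at 90% power.** For a fixed spread, the detectable effect scales with √(1/n₁ + 1/n₂) and with the sum of the normal quantiles.

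- Anchor from Section 9.2: 22% at 90% power for 80:54, where √(1/80 + 1/54) = 0.1761.
- 80:54 less 20% is 64:43, where √(1/64 + 1/43) = 0.1972. The effect becomes 22% × 0.1972 / 0.1761 = 24.6%.
- 93:62 less 20% is about 74:50. The effect becomes about 22.9%.
- Ratio of the 90% to the 80% effect at any N: (1.960 + 1.282) / (1.960 + 0.842) = 1.157. At 80:54 the 80% effect is 22% / 1.157 = 19.0%; at 64:43 it is 24.6% / 1.157 = 21.3%. The synopsis pair of 20% and about 25% fits neither exactly, since 20% × 1.157 = 23.1%.

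**3. Attack rate and power.** The placebo vAUC mean, SD and distribution are not given, so the 90% cannot be reproduced. The sensitivity check assumes a two-part model: vAUC is zero in the uninfected and normal or log-normal in the infected. The test is a simulated, tie-corrected Mann-Whitney test, two-sided at 0.05.

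Case A assumes that 22% at 90% power was derived at a 90% attack rate. This needs a coefficient of variation (CV) in the infected of about 0.325 (normal) or 0.344 (log-normal). Results at 83% attack:

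| Effect and type | 80:54 | 53:36 (two-thirds) |
|---|---|---|
| 22%, graded | about 76–79% | – |
| 26%, graded | about 90% | – |
| 30%, graded | about 96% | about 86% |
| 30%, all-or-none | about 71% | about 53–54% |

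Case B does not calibrate and varies the CV in the infected (log-normal, graded 22%, 80:54):

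| CV in infected | 90% attack | 83% attack |
|---|---|---|
| 0.25 | about 99% | about 94% |
| 0.30 | 95% | 87% |
| 0.40 | 80% | 67% |
| 0.50 | 64% | 50% |

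For CVs of 0.30 to 0.50 the fall from 90% to 83% attack costs about 8 to 14 points. The level depends on a spread that the documents do not give.

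**The case against.** **The power figures may be sound.** No passage says that the calculation used a 90% attack rate. Section 9.2 says only that placebo vAUC came from two earlier challenge studies. It contains no attack rate, so its absence from the version 5.0 list does not prove that the power was never rechecked. This stands. A reader might infer that the primary analysis has less power than stated, but the documents do not establish it: with a CV of 0.25 in the infected, power for 22% at 83% attack is still above 90%. Under a graded effect the 30% design target and the two-thirds statement also hold in Case A. They fall short only if efficacy is all-or-none, which Section 9.2 does not say.

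**The 22% and 25% may be one calculation with and without drop-out.** At 64:43 the 22% becomes 24.6%, and the synopsis mentions 20% drop-out in the next sentence. This is plausible, so a flat contradiction is not shown. Against it, the synopsis names 134 as the sample-size basis, and Section 9.2 applies drop-out to the vaccinated group, which gives 22.9%. What remains is that the N behind the synopsis figures is unstated.

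**The worst case.** A reader might also see an error in the statement that numbers "could be as low as 72 MVA-NP+M1 and 48 Placebo recipients" after a 25% reduction, because 75% of 93:62 is about 70:46. But Section 9.2 sets the 25% against 15% over-enrolment. The net 10% below 80:54 is 72 and 48.6, which gives the stated figures after rounding. This is loose wording, not a wrong number.

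**The zero-AUC count is exploratory.** The ELISpot correlation analysis in SAP 2.2.4 uses graphs and Spearman coefficients, not a contrast of zero against highest vAUC. That limits the harm but does not make 20 right.

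**Conclusion.** The zero-AUC figure is wrong as written. It should be about 34 of 80, about 14 of whom would be expected without vaccine, if the 30% is efficacy against infection and participants without an attack have zero vAUC. It is about 14 if the 30% is a graded reduction. Neither reading gives 20.

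The power statements need reconciling rather than retracting. The synopsis and Section 9.2/SAP 1.3 give different effects at 90% power, the N behind the synopsis figures is not stated, and no re-derivation is documented after the attack rate changed. The loss to about 76–79% power for a 22% effect, with about 26% detectable at 90% power, rests on two assumptions: that the stated figure was derived at 90% attack, and that the two-part model holds. It shows sensitivity and is not a replacement figure.

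The primary test, analysis population and sample size are unaffected.

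**What to change.** 1. In the synopsis and Section 9.1.2.3, replace the count with *about 34 of 80, of whom about 14 would be expected without vaccine*, and state that the 30% means efficacy against infection. Alternatively, keep 20 and label it as infections prevented.
2. Re-run the power calculation from the sponsor's placebo vAUC data at an 83% attack rate with the planned Mann-Whitney test. State whether the effect is graded or all-or-none.
3. Put one consistent set of figures in the synopsis, Section 9.2 and SAP 1.3, with N, attack rate and drop-out assumption beside each.

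The cost is a text change and one simulation, with no extra participants. The stated power may become less favourable.

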10. ADVERSE EVENT REPORTING

10.1 DEFINITIONS

Definition of Adverse Event

An AE is any untoward medical occurrence in a clinical study participant administered a medicinal (investigational or non-investigational) product. An AE does not necessarily have a causal relationship with the treatment. An AE can therefore be any unfavourable and unintended sign (including an abnormal finding), symptom, or disease temporally associated with the use of a medicinal (investigational or non-investigational) product, whether or not related to that medicinal (investigational or non-investigational) product.

This includes any occurrence that is new in onset or aggravated in severity or frequency from the baseline condition, or abnormal result of diagnostic procedures, including clinical laboratory test abnormalities.

Definition of Serious Adverse Event

An SAE is any untoward medical occurrence that at any dose meets any of the following conditions:

- results in death
- is life-threatening, i.e., the participant was at risk of death at the time of the event (e.g., ventricular fibrillation and anaphylaxis). The term does not refer to an event which hypothetically might have caused death if it were more severe.
- requires inpatient hospitalization or prolongation of existing inpatient hospitalization: Hospitalization refers to an overnight admission into hospital for the purpose of investigating and/or treating the AE. Hospitalization for an elective procedure, or routinely scheduled treatment for a pre-existing condition that has not worsened, is not an SAE.
- results in persistent or significant disability/incapacity, i.e., causing substantial disruption of the participant's ability to conduct normal life
- is a congenital anomaly/birth defect
- is medically significant, i.e., may not be immediately life-threatening or result in death or hospitalization but may jeopardize the participant's health or may require intervention to prevent one of the above outcomes. Examples of such events are intensive treatment in an emergency room or at home for allergic bronchospasm, blood dyscrasias, or convulsions that do not result in hospitalization or development of drug dependency or drug abuse.

Definition of Unlisted (Unexpected) Adverse Event

An AE is considered unlisted if the nature or severity is not consistent with the applicable product reference safety information in the Investigator Brochure.

Definition of Events of Special Interest

Adverse events of special interest (AESI) for this study are listed in [Appendix 1](#). AESI should be recorded and reported using the same procedures as for SAEs. They should therefore be recorded over the duration of the study to which the participant is recruited and reported to the Sponsor according to the process in [Section 10.7](#).

10.2 INTENSITY OF ADVERSE EVENTS

Each AE must be rated on a 5-point scale of increasing intensity according to the Common Terminology Criteria for Adverse Events (CTCAE) version 4.0:

Note: the semi-colon within the description of the grade indicates ‘or’.

Grade 1:

Mild; asymptomatic or mild symptoms; clinical or diagnostic observations only; intervention not indicated.

Grade 2:

Moderate; minimal, local or non-invasive intervention indicated; limiting age-appropriate instrumental activities of daily life (preparing meals, shopping for groceries or clothes, using the telephone, managing money, etc.).

Grade 3:

Severe or medically significant but not immediately life-threatening; hospitalization or prolongation of hospitalization indicated, disabling; limiting self-care activities of daily life (bathing, dressing and undressing, feeding self, using the toilet, taking medications, and not bedridden).

Grade 4:

Life-threatening consequences; urgent intervention indicated.

Grade 5:

Death related to AE.

10.3 CAUSALITY ASSESSMENT

Causality of each AE will be assessed according to the WHO-Uppsala Monitoring Centre (UMC) system for standardized case causality assessment.

Note: all of the assessment criteria per causality should be reasonably complied to.

Certain:

- Event or laboratory test abnormality with plausible time relationship to study drug.
- Cannot be explained by disease or other drugs.
- Response to withdrawal plausible (pharmacologically, pathologically).
- Event definitive immunologic or phenomenologically (i.e., an objective and specific medical disorder or a recognized pharmacological phenomenon).

Probable/Likely

- Event or laboratory test abnormality with reasonable time relationship to study drug administration
- Unlikely to be attributable to disease or other drugs.

Possible

- Event or laboratory test abnormality with reasonable time relationship to study drug administration
- Could also be explained by disease or other drugs.

Unlikely

- Event or laboratory test abnormality with a time to study drug administration that makes a relationship improbable (but not impossible)
- Disease or other drugs provide plausible explanations.

Not related

- Implausibly related to study intervention

